5.1 Primary objective

The primary objective is to document safety of pasireotide s.c. in patients with Cushing's disease (see [Section 3](#)).

5.1.1 Primary variable

The primary variable is the proportion of patients having a drug-related adverse event that was recorded as grade 3 or 4, or as a serious adverse event (see [Section on Adverse events](#) as to how the primary variable will be analyzed).

The analysis will be performed on the Safety set.

5.2 Secondary objectives

5.2.1 Efficacy objectives

These analyses will be performed on the FAS.

Mean 24h-UFC calculation

Screening urinary free cortisol will be measured in two or three 24-hour urine specimens collected during the screening period. The 24h-UFC concentration results from these two or three samples will be averaged to obtain the baseline UFC level. During the study, mean 24h-UFC will be determined at 4-week intervals until week 24. At week 4, 8, 16 and 20, mean 24h-UFC will be determined from two 24-hour urine collections collected on two consecutive days occurring before the visit. At week 12, 24 and 48, the mean 24h-UFC will be determined from two or three 24-hour urine collections, collected over the week before the visit. After week 24, the mean 24h-UFC will be determined at 12-week intervals until end of study visit, from two 24-hour collections during two consecutive days prior to each respective visit (except at Week 48).

Normalization of mean 24h-UFC at Week 12, 24 and 48

The endpoint associated with this objective is the proportion of patients achieving normalization of the mean 24h-UFC (UFC normalization), i.e. the mean 24h-UFC is $\leq 1.0 \times \text{ULN}$.

The number and percentage with corresponding two-sided 95% CI of patients achieving normalization of mean UFC mean 24h-UFC will be presented at Week 12, 24 and 48 (separately).

Note, the mean 24h-UFC is determined from two or three 24h-urine collections collected over the week before the visit.

Mean 24h-UFC imputation

If Week 24 mean 24h-UFC is missing then it will be imputed by the last available mean 24h-UFC values of at least two samples between and including Week 12 and Week 24. If Week 48 mean 24h-UFC is missing then it will be imputed by the last available mean 24h-UFC values of at least two samples between and including Week 12 and Week 48.

Summaries with and without imputing missing Week 24 and Week 48 mean 24h-UFC will be presented.

Similar analyses as defined above will also be performed at all other scheduled post-baseline assessments.

Reduction of mean 24h-UFC $\geq 50\%$ from baseline to Week 12, 24 and 48

The number and percentage with corresponding two-sided 95% CI of patients achieving a reduction of mean 24h-UFC $\geq 50\%$ from baseline to Week 12, 24 and 48 (separately) will be presented.

Similar analyses as defined above will also be performed at all other scheduled post-baseline assessments.

In addition, descriptive summaries of actual and percentage change in mean 24h-UFC from baseline to Week 12, 24 and 48 and all other scheduled post-baseline assessments will be provided.

Changes from baseline to Week 12, 24 and 48 in clinical signs and symptoms

The following clinical signs (Table 5-1) of Cushing's disease will be assessed by descriptive summaries of the change in systolic BP (standing and sitting), diastolic BP (standing and sitting), BMI, waist circumference and weight from baseline to each post-baseline visit. In addition, the proportion of patients satisfying the clinically relevant thresholds specified in the following table will be calculated along with the exact two-sided 95% CIs at each scheduled post-baseline assessment.

Table 5-1 Clinical Signs

Clinical Sign	Unit, Scale	Clinically relevant threshold (at any time point)
Standing Systolic BP	mmHg	≤ 140 mmHg
Sitting Systolic BP	mmHg, mean of 3 assessments	mean of 3 assessments ≤ 140 mmHg
Standing Diastolic BP	mmHg	≤ 90 mmHg
Sitting Diastolic BP	mmHg, mean of 3 assessments	mean of 3 assessments ≤ 90 mmHg
BMI	kg/m ² , Class levels: < 25.0, 25.0 to < 30.0, ≥ 30.0	% of patients reducing by at least one class level
Waist circumference	cm	Reduction of ≥ 5% Reduction of ≥ 10%
Weight	Kg	Reduction of ≥ 5%

Similar analyses as defined above will also be performed at all other scheduled post-baseline assessments.

The following clinical signs and symptoms (Table 5-2) of Cushing's disease will be assessed by descriptive summaries of changes (or shifts) from baseline to each scheduled post-baseline assessment. The corresponding method of analysis for each clinical sign and symptom are provided in the table.

Table 5-2 Clinical Signs and Symptoms

Clinical signs and symptoms	Scale	Analyses Methods
Facial Rubor (redness)	0=none, 1=mild, 2=moderate, 3=severe	Investigator interpretation, Counts & shifts from baseline.
Hirsutism (Ferriman-Gallway scoring)	0=minimum, 36=maximum Scoring in females only	Investigator interpretation, Ferriman-Gallway score, Actual and % change from baseline
Supraclavicular fat pads	0=none, 1=mild, 2=moderate, 3=severe	Investigator interpretation, Counts & shifts from baseline.
Dorsal fat pads	0=none, 1=mild, 2=moderate, 3=severe	Investigator interpretation, Counts & shifts from baseline.
Muscle strength	0=able to stand easily with arms extended, 1=able to stand after several efforts without using arms as assistance, 2=able to stand only by using arms as assistance 3=completely unable to stand	Direct observation of ability to stand unaided. Counts & shifts from baseline.
Striae	0=none, 1=mild, 2=moderate, 3=severe	Investigator interpretation, Counts & shifts from baseline.
Bruising	0=none, 1=mild, 2=moderate, 3=severe	Investigator interpretation, Counts & shifts from baseline.

Similar analyses as defined above will also be performed at all other scheduled post-baseline assessments.

Changes from baseline to Week 12 ,24 and 48 in Cushing Quality of Life scores

A 12-item Cushing's syndrome HRQoL questionnaire (CushingQoL, cf. [Webb et al 2008](#)) is implemented in this trial. Patients who completed 9 or more items at a visit are considered evaluable for that visit.

The list of questions includes the following and are answered using a categorical variable ranging from 1 to 5 (see Table 5-3):

1. I have trouble sleeping (I wake up during the night; it takes me a long time to get to sleep, etc.)
2. I have pain that keeps me from leading a normal life
3. My wounds take a long time to heal
4. I bruise easily
5. I am more irritable, I have sudden mood swings and angry outbursts
6. I have less self-confidence, I feel more insecure
7. I'm worried about the changes in my physical appearance due to my illness
8. I feel less like going out or seeing relatives or friends
9. I have had to give up my social or leisure activities due to my illness
10. My illness affects my everyday activities such as working or studying
11. It's difficult for me to remember things
12. I'm worried about my health in the future

Table 5-3 HRQoL ratings

Answers to HRQoL questions	Rating
'Always' or 'Very much'	1
'Often' or 'Quite a bit'	2
'Sometimes' or 'Somewhat'	3
'Rarely' or 'Very little'	4
'Never' or 'Not at all'	5

Standardized scores and their changes from baseline to Week 12, 24 and 48 will be descriptively summarized.

The standardized scores are calculated as follows:

1. Obtain raw scores, denoted by X, as the sum of all the ratings on all the HRQoL questions for a single patient and the score can range from 12 (worst HRQoL) to 60 points(best HRQoL).Therefore, the lower the score, the greater the impact on HRQoL.
2. Obtain standardized score, Y, for a single patient
 - a.
$$Y = 100 \cdot (X-12) / (60-12) = 100 \cdot (X-12)/48$$
. For example, if a patient answers all 12 items with 'Sometimes' or 'Somewhat', X = 36 and $Y = 100 \cdot 24/48 = 50$.

Similar analyses as defined above will also be performed at all other scheduled post-baseline assessments.

Changes from baseline to Week 12 , 24 and 48 in WPAI-GH scores

The WPAI-GH questionnaire is to assess work productivity and activity impairment.

WPAI outcomes are expressed as impairment percentages, with higher numbers indicating greater impairment and less productivity, i.e., worse outcomes, as follows (see [Reilly 2002](#)):

Questions:

- 1 = currently employed
- 2 = hours missed due to health problems
- 3 = hours missed other reasons
- 4 = hours actually worked
- 5 = degree health affected productivity while working
- 6 = degree health affected regular activities

Scores (multiply scores by 100 to express in percentages):

Percent work time missed due to health: $Q2/(Q2+Q4)$

Percent impairment while working due to health: $Q5/10$

Percent overall work impairment due to health:

$Q2/(Q2 + Q4)+[(1 - Q2/(Q2 + Q4)) \cdot (Q5/10)]$

[figure not shown]
Percent activity impairment due to health: $Q6/10$

Descriptive summaries of actual and percentage change in mean scores from baseline to Week 12, 24 and 48 will be provided. Similar analyses will also be performed at all other scheduled post-baseline assessments.

Changes from baseline in GH and IGF-I to Week 12, 24 and 48

Descriptive summaries of the absolute and relative change from baseline of GH and IGF-I at Week 12, 24 and 48 will be provided.

Similar analyses will also be performed at all other scheduled post-baseline assessments.

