disease from other forms of hypercortisolism, a confirmation of a pituitary source of ACTH secretion is needed. This includes an inappropriately normal or elevated plasma ACTH level and evidence of pituitary tumor on magnetic resonance imaging (MRI) scan or confirmed by bilateral inferior petrosal sinus sampling (BIPSS) after corticotrophin-releasing hormone (CRH) stimulation test (evidence of a pituitary source of ACTH). It is generally accepted that if the ratio of adrenocorticotrophin concentration in the inferior petrosal sinuses to peripheral-blood is greater than or equal to 3.0 after CRH stimulation, a diagnosis of Cushing's disease can be made ([Oldfield et al 1991](#)).

The incidence of Cushing's disease ranges from 1-3 patients per million per year.

Pituitary resection of the adenoma is the current first-line therapy for Cushing's disease, but surgical failure rates are as high as 25-30% even in the hands of the most experienced neurosurgeons. Additionally postoperative recurrence rates are as high as 20% by 5 years ([Bochicchio 1995](#), [Sonino 1996](#)). Surgery is in many cases complicated by hypopituitarism, which requires complicated life-long hormonal replacement therapy necessary to sustain life. Treatment usually focuses on replacing the target hormones rather than the pituitary hormones, and in patients who have multiple axis deficiencies maintenance with multiple replacement hormones can be difficult, and requiring close and constant medical monitoring, and can be expensive ([Swearingen et al 1999](#)).

Irradiation of the pituitary is another option but it may take many years to be effective and it is curative in only 15 to 45% of the cases. In addition, due to its lack of specificity the procedure also often results in panhypopituitarism. Furthermore, there is a 1 to 2% risk of development of secondary tumors in the field of radiation over subsequent years ([Orth 1995](#)).

[figure not shown]
When surgery and/or irradiation fail, or for those patients for whom such therapies are not an option, the remaining alternative is pharmacological treatment. No drug is currently approved for the treatment of Cushing's disease and the ones which physicians are using are fraught with suboptimal results and significant side effects ([Miller 1993](#), [Nieman 2002](#)) preventing their long term use required in the management of CD. Therefore, a safe and effective targeted medical therapy is highly desirable in this patient population.

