5.2 Inclusion criteria

Patients eligible for inclusion in this study have to meet **all** of the following criteria:

1. Written informed consent obtained prior to any screening procedures
2. Male or female patients aged 18 years or greater
3. Patients with confirmed diagnosis of Cushing's disease as evidenced by
 - mean urinary free cortisol of three 24-hour urine samples collected during the 3-week screening period above the upper limit of the laboratory normal range
 - morning plasma ACTH within the normal or above normal range
 - either MRI confirmation of pituitary adenoma (greater than or equal to 0.6 cm), or inferior petrosal sinus gradient >3 after CRH stimulation for those patients with a microadenoma less than 0.6 cm*, or for patients who have had prior pituitary surgery, histopathology confirming an ACTH staining adenoma. (* if IPSS had previously been performed without CRH (e.g. with DDAVP), then a central to peripheral pre-stimulation gradient > 2 is required. If IPSS had not previously been performed, IPSS with CRH stimulation is required)
4. Patients with de novo Cushing's disease must not be considered as candidates for pituitary surgery (i.e. poor surgical candidates, surgically unapproachable tumors, patients with no visible pituitary tumor, patients who refuse to have surgical treatment)
5. Karnofsky performance status >60 (i.e. requires occasional assistance, but is able to care for most of his personal needs)

6. For patients on previous medical treatment for Cushing's disease the following washout periods must be completed before screening assessments are performed
 - Inhibitors of steroidogenesis (e.g. ketoconazole, metyrapone, rosiglitazone): 1 week
 - Dopamine agonists (e.g. bromocriptine, cabergoline): 4 weeks
 - Mitotane: 6 months
 - Octreotide LAR and Lanreotide autogel: 8 weeks
 - Lanreotide SR: 4 weeks
 - Octreotide (immediate release formulation): 1 week
 - Glucocorticoid receptor inhibitor (mifepristone): 4 weeks

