5.3 Exclusion criteria

Patients eligible for this study must not meet **any** of the following criteria:

1. Radiotherapy of the pituitary <4 weeks before screening or patient who has not recovered from side effects
2. Patients with compression of the optic chiasm causing acute clinically significant visual field defect
3. Patients with Cushing's syndrome due to ectopic ACTH secretion
4. Patients with hypercortisolism secondary to adrenal tumors or nodular (primary) bilateral adrenal hyperplasia
5. Patients who have a known inherited syndrome as the cause for hormone over secretion (i.e. Carney Complex, McCune-Albright syndrome, MEN-1)
6. Patients with a diagnosis of glucocorticoid-remedial aldosteronism (GRA)
7. Patients who have undergone major surgery within 1 month prior to screening
8. Patients with known gallbladder or bile duct disease, acute or chronic pancreatitis (patients with asymptomatic cholelithiasis and asymptomatic bile duct dilation can be included)
9. Diabetic patients whose blood glucose is poorly controlled as evidenced by $\text{HbA}_{1\text{C}} > 8\%$
10. Patients who have clinically significant impairment in cardiovascular function or are at risk thereof, as evidenced by
 - congestive heart failure (NYHA Class III or IV), unstable angina, sustained ventricular tachycardia, clinically significant bradycardia, high grade AV block, history of acute MI less than one year prior to study entry
 - QTcF >450 msec at screening
 - History of syncope or family history of idiopathic sudden death
 - Risk factors for Torsades de Pointes such as uncorrected hypokalemia, uncorrected hypomagnesemia, cardiac failure
 - Concomitant disease(s) that could prolong the QT interval such as autonomic neuropathy (caused by diabetes or Parkinson's disease), HIV, cirrhosis, uncontrolled hypothyroidism, concomitant medication(s) with known risk for TdP
11. Patients with liver disease or history of liver disease such as cirrhosis, chronic active hepatitis B and C, or chronic persistent hepatitis, or patients with ALT or AST more than

2 x ULN, serum creatinine >2.0 x ULN, serum bilirubin >1.5 x ULN, serum albumin < 0.67 x LLN at screening

12. Patients who have any current or prior medical condition that can interfere with the conduct of the study or the evaluation of its results, such as

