6.3.1 Permitted concomitant therapy

The patient must be told to notify the investigational site about any new medications he/she takes after the start of the study drug. All medications (other than study drug) and significant non-drug therapies (including physical therapy and blood transfusions) administered during the study must be listed on the Concomitant Medications or the Procedures and Significant Non-Drug Therapies CRF, respectively.

Diabetic patients must continue their treatment for diabetes throughout the study as indicated by their physician/diabetes specialist.

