6.3.2 Prohibited concomitant therapy

Rosiglitazone and pioglitazone treatment are not permitted during the study as they could affect the patient's ACTH levels.

Further, the use of concomitant medications with known risk of TdP is prohibited and requires the discontinuation of the patient prior to starting the respective medication with known risk of TdP. The list of updated medications with known risk of TdP can be found at the following link: <http://crediblemeds.org/>

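### A patient kept on pasireotide and normalised by an added cortisol-lowering treatment counts as a pasireotide UFC responder, because most such drug classes are not barred on study and the SAP has no rule for them

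*SAP*

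**What the plan says.** **Before entry.** Protocol 5.2 criterion 6: "For patients on previous medical treatment for Cushing's disease the following washout periods must be completed before screening assessments are performed". The list covers steroidogenesis inhibitors, dopamine agonists, mitotane, octreotide and lanreotide, and mifepristone. Protocol 7.1.1 adds that washout must be finished before the screening samples are taken.

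**On study.** Protocol 6.3.2 has two prohibitions. The first begins "Rosiglitazone and pioglitazone treatment are not permitted during the study as they could affect" and gives an effect on ACTH as the reason. The second covers drugs with known torsades risk, and refers to an external list. Protocol 6.3 asks investigators to discourage other medication, except to treat an adverse event. Protocol 6.3.1 requires recording: "All medications (other than study drug) and significant non-drug therapies (including physical therapy and blood transfusions) administered during the study must be listed" on the relevant CRF pages.

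**Withdrawal.** Protocol 7.1.3.1 requires withdrawal for lack of efficacy when UFC stays high and there is also no clinical benefit after at least 3 months. Apart from torsades-risk drugs, starting another treatment for Cushing's disease is not on the list.

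**Analysis.** SAP 5.2.1 defines the endpoint: "The endpoint associated with this objective is the proportion of patients achieving normalization of the mean 24h-UFC (UFC normalization". It is analysed on the FAS, which SAP 4.6.1 defines as everyone dosed. The only rule on handling UFC values carries the last available mean from Week 12 onwards into a missing Week 24 or Week 48. SAP 5.5 tabulates concomitant therapy on the safety set, without linking it to UFC response.

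**The concern.** The secondary objective is to document what pasireotide does to UFC. With a single arm, no control group shows what other treatment contributes. The protocol recognises the problem at entry through the washout, and on study for the glitazones. It does not carry the same reasoning to the other washed-out classes, and the SAP does not make up for it.

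The patients most exposed are those with partial benefit and UFC still above normal, since they are plausible candidates for added treatment. Any misattribution would then raise the normalisation rate, and the rate of reduction by at least 50%, more at Weeks 24 and 48 than at Week 12. A reader of the final tables could not tell how many responders, if any, arose this way.

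**Working it through.** The plan has no figure of its own to reproduce: about 200 patients were planned from accrual (SAP 4.10.1) and no hypothesis is tested (Protocol 10.4.2). The check follows one patient through the rules and then sizes one such case.

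**Step 1. Can the patient stay on study?** Take a patient whose UFC remains above normal on pasireotide, with some clinical benefit. The lack-of-efficacy criterion needs both elevated UFC and no benefit, so withdrawal is not required. Protocol 1.2.1 says benefit in the earlier phase III study was seen whether or not UFC normalised, so such patients are to be expected.

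**Step 2. Can another treatment be added?** A dopamine agonist, for example, belongs to a class in criterion 6. Protocol 6.3.2 does not name the class. Unless the particular drug is on the external torsades list, adding it is discouraged and recorded, but neither prohibited nor a reason for withdrawal. No section addresses pituitary or adrenal surgery on study.

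**Step 3. How is the later UFC counted?** If the mean is at or below normal at Week 24 or 48, SAP 5.2.1 counts a response. There is no per-protocol set (SAP 4.6), so recording a deviation under SAP 5.4.1 removes nobody from the rate.

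**Step 4. Can the value spread?** Yes. With Week 48 missing, a Week 36 mean obtained under the added treatment qualifies as the carried-forward value.

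**Step 5. Size.** SAP section 5 bases percentages on the relevant population. At the planned 200, one patient contributes 1/200 = 0.5 percentage points.

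For k such patients the reported rate is (x + k)/200, where x is the number of responders without added treatment. The documents give no k, so the table assumes 4, 10 or 20 patients (2%, 5%, 10%). For x it borrows the two month-6 rates in Protocol 1.2.1: 200 × 0.146 = 29.2, taken as 29, and 200 × 0.263 = 52.6, taken as 53. Intervals are exact 95% (Clopper-Pearson), as in SAP 4.12.1.1.

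| k (assumed) | x = 29 | x = 53 |
|---|---|---|
| 0 | 14.5% (9.9–20.2) | 26.5% (20.5–33.2) |
| 4 | 16.5% (11.6–22.4) | 28.5% (22.4–35.3) |
| 10 | 19.5% (14.2–25.7) | 31.5% (25.1–38.4) |
| 20 | 24.5% (18.7–31.1) | 36.5% (29.8–43.6) |

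These rows show how the rate responds to k. They do not estimate the bias. The borrowed rates come from patients with UFC above 1.5 times the upper limit and count response without up-titration. Neither condition applies here.

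**The case against.** The protocol is tighter than the prohibited list alone suggests. Rosiglitazone, which criterion 6 names, is barred on study, as is anything on the torsades list. Other medication is discouraged. In EU countries, the stated step for an uncontrolled patient is a dose increase (Protocol 6.2.1). Permanently stopping pasireotide ends participation (Protocol 6.2.2 and 7.1.3), so a patient who switches drug or stops for surgery leaves the study. All of this stands. It narrows the problem to treatment added on top of continued pasireotide, but does not change how a UFC value is counted.

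A reader might infer more in four ways, and the documents do not support them:

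- **That every washed-out drug is freely allowed.** Some are barred. How many cannot be checked, because the torsades list is not reproduced.
- **That irradiation inflates Week 24 or Week 48.** Of irradiation, Protocol 1.1 says "it may take many years to be effective and it is curative in only 15 to 45% of the cases", which argues against an effect that soon from irradiation started on study. Earlier irradiation is a baseline characteristic, since the exclusion reads "Radiotherapy of the pituitary <4 weeks before screening or patient who has not recovered from side effects" and raised UFC is still required at entry. SAP 4.7 sends subgroups to a section 6 that is not in the text available, so a missing split by prior irradiation cannot be asserted.
- **That glucocorticoid replacement distorts the endpoint.** The sections on hypoadrenalism provide for dose reduction, and withdrawal if it persists. They do not mention replacement, so a special rule would be speculative.
- **That the response rate is overstated by a known proportion.** Any such proportion only restates the assumed inputs.

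It is also fair that an all-values summary is legitimate in a descriptive expanded-access study whose primary objective is safety. It should therefore be kept, but on its own it cannot show how much of the response arose under other treatment.

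**Conclusion.** The point holds in a limited form. Most drug classes washed out under criterion 6 are not prohibited as a class during treatment, surgery added on study is not addressed, and SAP 5.2.1 attributes any later normal UFC to pasireotide. It affects two secondary, descriptive responder endpoints, not the primary safety endpoint or any error rate.

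The size is 0.5 percentage points per affected patient at 200 patients. The number affected is unknown and could be zero. The conclusion about the missing rule rests on the visible text. Protocol 10.6 is redacted, SAP section 6 is not available and the deviation criteria sit in a separate document. SAP 4.7 limits subgroups to characteristics measured before inclusion, so section 6 would not be expected to cover treatment added later. It is worth correcting because the remedy is cheap and would show whether the issue arose at all.

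**What to change.** In SAP 5.2.1:

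1. From the Concomitant Medications and the Procedures and Significant Non-Drug Therapies CRFs, derive a flag with date for the first on-study start of any drug class in criterion 6, or of pituitary or adrenal surgery or irradiation.
2. Report how many patients are flagged by Weeks 12, 24 and 48.
3. For normalisation and for reduction of at least 50%, add a summary that counts visits after that date as non-response and does not use values from those visits as carried-forward donors.
4. Show it beside the current all-values summary.

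Separately, Protocol 5.2 criterion 6 and Protocol 6.3.2 must be reconciled. Which treatments are allowed on study is for the sponsor's clinical team to settle.

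The cost is one derived variable and some extra table columns, from data already collected. The response rate in the added summary may be slightly lower. The rule is conservative for a patient who was already normal before the added treatment, which is a reason to show both summaries. If the database is already locked, SAP section 1 requires the change to be documented separately.

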2.3 Rationale for dose and regimen selection

Results from the pivotal study [SOM230B2305] showed that the 900 µg b.i.d dose met the primary endpoint and can be used as a starting dose. In addition, it was observed that patients with impaired glucose metabolism had a less pronounced increase in blood glucose when using the 600 µg b.i.d dosing. [Applicable for countries outside the European Union] Therefore, this study will use the 900 µg b.i.d as starting dose in all patients except the ones affected by impaired glucose metabolism that will have the 600 µg b.i.d as starting dose

[Applicable for countries in the European Union] Based on the positive opinion and recommendation from CHMP on 19 January 2012, the starting dose of commercial pasireotide s.c for the treatment of Cushing's disease will be 600 µg b.i.d for all patients coming from European Union countries. Accordingly, the starting dose in this study will be 600 µg b.i.d in all patients (including the ones affected by impaired glucose metabolism) with the option to increase the dose to 900 µg b.i.d. if the patient is not controlled (i.e. 24h-mean UFC levels above the upper limit of normal) at earliest after 2 months of treatment provided the 600 µg b.i.d dose is well tolerated by the patient. However patients on going in the study at the time of approval of amendment 3 will continue on their current dose.

3 Objectives and endpoints

Objectives and related endpoints are described in [Table 3-1](#) below.

Table 3-1 Objectives and related endpoints

Objective	Endpoint	Analysis
Primary		Refer to Section 10.4 .
To document the safety of pasireotide s.c. in patients with CD	The proportion of patients having a drug-related adverse event that is recorded as grade 3 or 4 or as a serious adverse event.	
Secondary		Refer to Section 10.5.1 .
To document the efficacy of pasireotide s.c. in normalizing mean 24h-UFC at Week 12, 24 and 48, separately	The proportion of patients with mean 24h-UFC \leq ULN at Week 12, 24 and 48, separately	
To document the efficacy of pasireotide s.c. in achieving at least 50% reduction of mean 24h-UFC from baseline at Week 12, 24 and 48, separately	The proportion of patients achieving a reduction of mean 24h-UFC \geq 50% from baseline at Week 12, 24 and 48, separately	
To document the changes in clinical signs and symptoms	The change from baseline to Week 12, 24 and 48 in clinical signs and symptoms	

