10.5.1.5 Clinical signs and symptoms

The following clinical signs of Cushing's disease will be assessed by descriptive summaries of the change in systolic BP (standing and sitting), diastolic BP (standing and sitting), BMI, waist circumference and weight from baseline to each post-baseline visit. In addition, the proportion of patients satisfying the clinically relevant thresholds specified in the following

table will be calculated along with the exact two-sided 95% CIs at each scheduled post-baseline assessment.

Clinical signs	Unit, Scale	Clinically relevant threshold (at any timepoint)
Standing Systolic BP	mmHg	≤ 140 mmHg
Sitting Systolic BP	mmHg, mean of 3 assessments	mean of 3 assessments ≤ 140 mmHg
Standing Diastolic BP	mmHg	≤ 90 mmHg
Sitting Diastolic BP	mmHg, mean of 3 assessments	mean of 3 assessments ≤ 90 mmHg
BMI	kg/m ² , Class levels: < 25.0, 25.0 to < 30.0, ≥ 30.0	% of patients reducing by at least one class level
Waist circumference	cm	Reduction of ≥ 5% Reducing of ≥ 10%
Weight	Kg	Reducing of ≥ 5%

The following clinical signs and symptoms of Cushing's disease will be assessed by descriptive summaries of changes and shifts from baseline to each scheduled post-baseline assessment. The clinical signs and symptoms that will be analyzed and the corresponding methods of analyses are provided in the following table.

Clinical signs and symptoms	Scale	Analyses methods
Facial Rubor (redness)	0=none, 1=mild, 2=moderate, 3=severe	Investigator interpretation, Counts & shifts from baseline.
Hirsutism (Ferriman-Gallway scoring)	0=minimum, 36=maximum Scoring in females only	Investigator interpretation, Ferriman-Gallway score, Actual and % change from baseline
Supraclavicular fat pads	0=none, 1=mild, 2=moderate, 3=severe	Investigator interpretation, Counts & shifts from baseline.
Dorsal fat pads	0=none, 1=mild, 2=moderate, 3=severe	Investigator interpretation, Counts & shifts from baseline.
Muscle strength	0= able to stand easily with arms extended, 1 = able to stand after several efforts without using arms as assistance, 2=able to stand only by using arms as assistance 3= completely unable to stand	Direct observation of ability to stand unaided. Counts & shifts from baseline.
Striae	0=none, 1=mild, 2=moderate, 3=severe	Investigator interpretation, Counts & shifts from baseline.
Bruising	0=none, 1=mild, 2=moderate, 3=severe	Investigator interpretation, Counts & shifts from baseline.

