4.6 Analysis sets

4.6.1 Full analysis set

The Full Analysis Set (FAS) comprises all patients who received at least one dose of pasireotide s.c.

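### The four blood-pressure threshold proportions in SAP Table 5-1 are post-baseline prevalences with no baseline figure beside them, so they cannot be read as change or normalisation

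*SAP*

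**What the plan says.** The secondary endpoint in protocol Table 3-1 is "The change from baseline to Week 12, 24 and 48 in clinical signs and symptoms". SAP 5.2.1 (Table 5-1), matching protocol 10.5.1.5 in substance, serves it in two ways.

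- **Change summaries.** The signs are to be "assessed by descriptive summaries of the change in systolic BP (standing and sitting), diastolic BP (standing and sitting), BMI, waist circumference and weight"; this is planned for every visit after baseline.
- **Threshold proportions.** As an addition, the SAP plans "the proportion of patients satisfying the clinically relevant thresholds specified in the following" table, with exact two-sided 95% intervals, at each scheduled post-baseline assessment.

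The sitting blood-pressure criteria are "mean of 3 assessments ≤ 140 mmHg" and "mean of 3 assessments ≤ 90 mmHg"; the standing rows use the same cut-offs on the standing reading. None of the four has a baseline condition. The other rows of the table do refer to baseline: BMI is the percentage "of patients reducing by at least one class level", and waist and weight are percentage reductions.

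On the population, SAP 5.2.1 states "These analyses will be performed on the FAS", and SAP 4.6.1 states "The Full Analysis Set (FAS) comprises all patients who received at least one dose of pasireotide s.c". SAP Section 5 takes percentages over the relevant population or subgroup unless otherwise noted.

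**The concern.** No inclusion criterion in protocol 5.2 requires raised blood pressure. A patient who is at or below 140/90 mmHg at baseline and stays there is therefore counted at every visit as satisfying the threshold. The result mixes patients who came down to the threshold with patients who were never above it. Without the baseline proportion, the reader cannot separate the two.

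Elsewhere the plan avoids this:

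- UFC normalisation also uses an absolute cut-off, but entry requires mean UFC above the upper limit of normal, so every eligible patient starts abnormal.
- The absolute QTc categories in SAP 5.3.5.1 require the patient to be at or below the cut-off at baseline.
- Clinically notable blood pressure in SAP 5.3.4 requires a change from baseline as well as a level.

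At stake is interpretation. In a single-arm study, a high proportion with an exact interval, under a heading about changes from baseline, is easily taken as evidence of improvement.

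**Working it through.** The plan states no figure to reproduce: there is no sample size calculation and no hypothesis test. What follows is illustration. N = 200 is the planned size (SAP 4.10.1). All shares and rates are assumptions, because the documents give none.

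**1. Blood pressure, all patients.** Let q be the share at or below the threshold at baseline, c the share of those above it who normalise, and l the share of those at or below it who lose control.

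Reported proportion = q(1 − l) + c(1 − q)

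| q | No change (c = 0, l = 0), exact 95% CI | c = 20%, l = 0 | c = 20%, l = 10% | c = 50%, l = 0 |
|---|---|---|---|---|
| 40% | 80/200 = 40% (33.2 to 47.1) | 52% | 48% | 70% |
| 60% | 120/200 = 60% (52.9 to 66.8) | 68% | 62% | 80% |
| 70% | 140/200 = 70% (63.1 to 76.3) | 76% | 69% | 85% |

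For example, at q = 60%, c = 20% and l = 10%: 0.60 × 0.90 + 0.20 × 0.40 = 0.54 + 0.08 = 62%. A cohort with q = 70% and no change in anyone reports 70%. That is more than a cohort with q = 60% in which a fifth of the patients above threshold normalise (68%).

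**2. Blood pressure, only patients above threshold at baseline.** Restricting the denominator is not a clean answer by itself. Assume baseline and follow-up readings are bivariate normal with the same mean and variance (no effect), and with correlation 0.8 to 0.5. The share of the selected patients who fall to the threshold or below is then:

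- q = 40%: about 17% to 27%
- q = 60%: about 25% to 40%
- q = 70%: about 30% to 48%

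This is regression to the mean. The opposite flow reveals it. At q = 60% and correlation 0.8, about 24.8% of 80 patients above threshold come down (about 20), and about 16.5% of 120 at or below go up (about 20). Net change is zero. Showing both directions lets a reader see this; showing normalisation alone does not.

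**3. BMI.** Let b be the share with baseline BMI below 25.0 and r the share of the remainder who drop a class.

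Reported proportion = r(1 − b)

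With no change it is 0% for every b, so patients already below 25.0 never count as successes. They only enlarge the denominator: r = 20% is reported as 18%, 16%, 14% or 12% for b = 10%, 20%, 30% or 40%, and the maximum is 1 − b. At b = 20% and N = 200, this is 32/200 = 16.0% (11.2 to 21.8) over all patients, against 32/160 = 20.0% (14.1 to 27.0) among those who can drop a class.

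**The case against.** The strongest reply is that the endpoint is already measured. The same paragraph plans change-from-baseline summaries for every sign in the table, and the proportions are an addition. This stands. A reader might infer that the plan fails to document change in blood pressure; it does not. What a mean change cannot show is how many patients crossed the threshold in each direction, which is the natural use of a threshold table.

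Second, the share of patients at or below 140/90 mmHg at a visit is a legitimate prevalence, and the documents call the criteria clinically relevant thresholds, not response. This also stands: the planned figure is not wrong in itself. It lacks the comparator needed under a heading about change.

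Third, a reader might extend the criticism to BMI. The documents do not support that. The BMI criterion is a drop in class from baseline, and a patient below 25.0 cannot meet it. The only issue is dilution, and an all-patient denominator is a defensible choice.

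Fourth, replacing the all-patient figure with one restricted to patients above threshold would bring in regression to the mean and hide loss of control. This is correct, and it determines the form of the fix.

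Finally, SAP Section 6 (subgroup analyses) is not in the text available for review, so a split by baseline blood pressure there cannot be excluded. All analyses are descriptive and the primary endpoint is safety, so no error rate or power is affected.

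**Conclusion.** The point holds for the four blood-pressure rows. They give the proportion at or below a level after baseline, with the baseline share built in and not shown. With no change in any patient they return that share: 40% to 70% over the assumed range. How far the figures would mislead depends on the true share and on movement in both directions, neither of which the documents give.

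The defect is limited to these supplementary proportions. It touches neither the change-from-baseline summaries nor the primary analysis. For BMI there is only a minor dilution. This is an inexpensive improvement to interpretability, not a flaw that threatens the study's conclusions.

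**What to change.** In SAP 5.2.1, for each of the four blood-pressure rows:

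- Print the baseline proportion beside each visit's proportion, in the same patients (those with both values).
- Add a baseline-by-visit shift table (at or below versus above threshold). From it report normalisation among patients above threshold at baseline and loss of control among those at or below it, each with an exact 95% interval.
- Add a note that the normalisation figure is subject to regression to the mean and should be read with the loss-of-control figure.

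For BMI, keep the planned proportion and also report it among patients with baseline BMI of at least 25.0.

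All of this uses data already collected. The cost is SAP wording, a baseline flag and slightly more tabulation. The subset figures will have smaller denominators and wider intervals.
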